1.4.4 Risk of Nasal Swab

The primary risk of a nasal swab is local discomfort. Rarely, there can be local bleeding from the nasal mucosa, which is controlled with local measures such as pressure or packing with gauze.

1.4.5 Benefits

There may be no benefits to individual subjects for participation in this study, but the information may lead to generalizable knowledge about influenza. There may be earlier resolution of symptoms or fewer complications from influenza in those who are randomized to the active treatment arm, but benefit is not guaranteed.

1.4.6 Alternatives

The alternative to participation in this study is routine standard care. For uncomplicated influenza this may be no therapy or may be an antiviral (likely oseltamivir or zanamivir based largely on availability and susceptibility).

2 STUDY OBJECTIVES

2.1 Primary Objective

The overall objective of the study is to evaluate the antiviral efficacy of oseltamivir compared to placebo in the treatment of subjects with confirmed influenza infection (Primary Efficacy Population) as measured by percentage of subjects with virus detectable by PCR in NP swab at Day 3.

2.2 Secondary Objectives

1. Evaluate the antiviral efficacy of treatment with oseltamivir compared with placebo in those subjects with confirmed influenza infection (primary efficacy population) and intention to treat (ITT) population as assessed by the following parameters:

Virologic: (by PCR in NP swab)

- AUC of viral shedding
- Duration of viral shedding
- Percent cessation of viral shedding on Days 3 and 7
- Frequency of emergence of antiviral resistance

Clinical:

- Time to alleviation of influenza clinical symptoms
- Time to absence of fever
- Time to resolution of all symptoms AND fever
- Time to resumption of normal activity
- Proportion of subjects who require hospitalization
- Proportion of subjects who develop bronchitis, pneumonia, or other complications of influenza

2. Evaluate the association of viral shedding (both qualitative and quantitative) to clinical symptoms and fever.

3. Evaluate if changes in viral shedding by antiviral treatment predict changes in clinical symptoms and fever.

4. Evaluate subject self-collected nasal samples compared with study team collected samples for the determination of viral shedding.

5. Evaluate the variability in the sample collection. (pilot study only)

6. Evaluate the association of viral shedding as assessed by TCID₅₀ to viral shedding as assessed by qualitative PCR. (pilot study only)

3 INVESTIGATIONAL PLAN

3.1 Overview of Study Design

The purpose of this randomized blinded study is to evaluate whether oseltamivir modifies viral shedding in an ambulatory population with uncomplicated influenza. This study is also designed to explore the relationship between virologic effects and clinical effects, effects on pro-inflammatory mediators, and to start understanding if improvements to virologic shedding correlate with improvements in clinical outcomes. For this reason, the study is powered to show an anticipated difference in virologic shedding. This is a multicenter international study. Up to approximately 50 sites may participate in this protocol.

It is anticipated that about 800 subjects may be enrolled to allow 560 eligible subjects to be randomized in this study. The anticipated study duration is 7 years. The original sample size of the study was powered to show a difference in virologic shedding as detected by TCID₅₀ (as detailed in Section 9.2). With new virologic techniques such as PCR, it is anticipated that the objectives of this study may be achievable with smaller numbers of subjects; therefore the sample size has been reduced.

Subjects with an influenza-like illness will be screened for the study, and those found positive for influenza will be randomized in a 1:1 manner to receive a blinded study treatment consisting of either oseltamivir or placebo for 5 days. The study arms are as follows (Table 2):

Table 2: Treatment Allocation

| Arm | Drug | Allocation Ratio | Capsule |
|-----|---------------------|------------------|-------------|
| 1 | Oseltamivir | 1 | Oseltamivir |
| 2 | Oseltamivir placebo | 1 | Placebo |

Subjects will be assessed on Study Day 0 (pre-dose), and on Study Days 3, 7, and 28. All subjects will undergo a series of efficacy and safety assessments during the study. Blood samples will be collected on Days 0, 3, 7, and 28.

Table 4 in Section 6 presents the schedule of assessments. A detailed presentation of assessments to be conducted at each visit is presented in Section 6.3.

The first 50 subjects randomized were part of a pilot study to help determine the optimal virologic endpoint to be used in the efficacy analysis. These subjects had duplicate virologic samples on Day 0 to determine reproducibility. Additionally, all virologic samples from these subjects were tested by both PCR and culture (TCID₅₀), and the results were analyzed by several different methods as outlined in a separate virology sample analysis plan. This allowed determination of the reproducibility of the virologic assays, and measure the distribution, variance, and presence and impact of missing data (see Section 9.5 for more details on the statistical considerations of the pilot study).

From this pilot study the primary endpoint was determined to be the percentage of subjects with virus detectable by PCR in NP swab at Day 3.

The data collected in this study are essentially identical as for IRC-003. Therefore, the cumulative database will encompass the spectrum of ambulatory influenza (those at risk and those not at risk, as well as placebo, monotherapy, and combination therapy treated).

Additionally, this study will explore the utility of subject self-collected samples. If self-collected samples provide the same quantitative information as study team-collected samples, self-collected samples could be utilized in future studies for more frequent assessment of viral shedding with fewer clinic visits. For this study, a subject self-collected sample will be obtained once daily on Study Days 0, 1, 2, and 3.

3.2 Definitions for the Purpose of this Study

Enrolled

For the purpose of collecting data and samples, and reporting AEs, a subject will be considered enrolled beginning from the time the informed consent form is signed until the subject is considered “screen failure,” “discontinued,” or “completed.”

Randomized

Subjects are considered randomized when they meet all of the following criteria:

- Confirmation that the inclusion and exclusion criteria are met
- Consent is given and signed by the subject for the study
- Randomization number is assigned

Screen Failures

Subjects are considered screen failures when they meet one of the following criteria after signing consent:

- Screening tests reveal that the subject is ineligible
- Subject withdraws consent before being randomized

Discontinued

Subjects are considered discontinued when they meet one or more of the following criteria:

- Subject withdraws consent after being randomized (see Section 4.6)
- Subject is withdrawn after enrollment by investigator (see Section 4.8) including lost to follow-up

Completed

Subjects are considered completed when they are followed through Study Day 28 and complete the final study follow-up visit (Study Day 28) or die prior to this study visit.

3.3 Study Endpoints

3.3.1 Primary Endpoint

Percentage of subjects shedding virus by PCR in NP swab at day 3.

3.3.2 Secondary Endpoints

Clinical Endpoints:

- Time to alleviation of influenza clinical symptoms
- Time to absence of fever
- Time to resumption of normal activity
- Number of premature study treatment discontinuations
- Proportion of subjects who develop bronchitis, pneumonia, or other complications of influenza
- Proportion of subjects who require hospitalization
- 28-day mortality

Virologic Endpoints: (assessed by PCR in NP swab)

- Duration of viral shedding
- Change in viral shedding as a function of time
- AUC of viral shedding
- Frequency of emergence of antiviral resistance

3.3.3 Endpoint Definitions

- Duration of viral shedding as assessed by PCR is defined as time to reduction of qPCR to below limit of detection, at the first of two successive measurements.
- Development of resistance is defined as the percentage of subjects who develop a resistant strain population by day 7, as measured by RNA sequencing of NA for recognized oseltamivir resistance mutations (e.g., H275Y or N295S in N1, R292K or E119V in N2).
- Duration of clinical symptoms is defined as the time to alleviation of all clinical symptoms to 0 (absent) or 1(mild) on two successive measurements in absence of symptom relief medications.
- Absence of fever (temperature <38.0°C/100.4°F) for 24 hours without antipyretic.
- Time to resumption of normal activity is defined as time to the time to the first “yes” answer to the global assessment question “Are you functioning as well as you were before you had the flu?” (Section 7.3.1.4).

4 STUDY POPULATION

4.1 Rationale for Research Subject Selection

The subject population includes those at low risk for complications and morbidity from influenza (as defined by the U.S. CDC), and have a diagnosis by rapid antigen or PCR of influenza. Exclusions are primarily to increase subject safety.

4.1.1 Justification of Exclusions of Pregnant Women and Children

Pregnant women with influenza are recommended to be treated with oseltamivir or zanamivir, therefore, randomization of a pregnant woman to possibly receive placebo could not be justified. The protocol does not provide access to any treatment that children cannot currently receive, and therefore children are excluded from participation.

4.2 Recruitment

It is anticipated that subjects will primarily be recruited through emergency rooms, medical clinics, or other health care settings (e.g., university health clinics) that would be first contact of subjects with influenza. Information about this study will be disseminated to health care providers in these settings. Additionally, direct-to-subject recruitment (using posters and/or other informational items) may occur in these settings.

Any direct-to-subject recruitment will be submitted to the reviewing Institutional Review Board (IRB)/Independent Ethics Committee (IEC) for approval. Informational items about the study that will be circulated to health care staff only are not required to be reviewed by the IRB/IEC.

4.3 Inclusion Criteria for Enrollment (Screening)

1. Signed informed consent prior to initiation of any study procedures
2. Age ≥ 18 and < 65 years of age
3. One or more respiratory symptoms (cough, sore throat, or nasal symptoms)
4. Onset of respiratory symptoms no more than 48 hours before enrollment (screening)
5. Willingness to have samples stored

4.4 Inclusion Criteria for Randomization

Positive test for influenza (either rapid antigen or PCR)

- Randomization may proceed in cases of discrepant results (one positive and one negative)

NOTE: Results from laboratory tests obtained for clinical indications within 24 hours before screening/enrollment may be used if available.

4.5 Exclusion Criteria (for Enrollment or Randomization)

1. Hospitalization at the time of enrollment
2. Presence of a medical condition(s) that has been associated with increased risk of complications from influenza
 - Age 65 years of age or older
 - Asthma
 - Neurological and neuro-developmental conditions (including disorders of the brain, spinal cord, peripheral nerve, and muscle such as cerebral palsy, epilepsy [seizure disorders], stroke, moderate to severe developmental delay, muscular dystrophy, or spinal cord injury)
 - Chronic lung disease (such as COPD and cystic fibrosis)
 - Heart disease (such as congenital heart disease, congestive heart failure, and coronary artery disease). Hypertension or mild arrhythmia alone would not be considered exclusionary
 - Blood disorders
 - Endocrine disorders (such as diabetes mellitus)
 - Kidney disorders
 - Liver disorders

- Metabolic disorders (such as inherited metabolic disorders and mitochondrial disorders)
 - Weakened immune system due to disease or medication (such as people with HIV/AIDS, or cancer, chronic steroids or other medications causing immune suppression)
 - Pregnant or 4 weeks postpartum
 - BMI \geq 40
3. Breastfeeding
 4. Inability to take oral medication or a history of GI malabsorption which would preclude the use of oral medication.
 5. Received more than one dose of any antiviral influenza medications since onset of influenza symptoms
 6. Known end stage renal dysfunction or creatinine clearance less than 60 mL/min
 7. Known hypersensitivity to oseltamivir, peramivir, or zanamivir
 8. Received live attenuated influenza virus vaccine within 3 weeks prior to study entry
 9. Use of any investigational drug within 30 days or 5 half-lives (whichever is longer) prior to study entry
 10. Participation in other research protocols that require more than 100 mL of blood to be drawn in any 4-week period that overlaps with this study.

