1 BACKGROUND INFORMATION AND SCIENTIFIC RATIONALE

1.1 Influenza Infections in Humans

1.1.1 Epidemiology

Influenza causes annual epidemics of acute respiratory illness. Most people who get influenza will recover in a few days to less than 2 weeks, but some people will develop complications (such as pneumonia) as a result of influenza, some of which can be life-threatening and result in death. Complications from influenza can happen at any age, but some people are at higher risk of developing serious influenza-related complications. People at higher risk include people 65 years and older, people of any age with certain chronic medical conditions (including asthma, diabetes, immunosuppression, and heart disease), pregnant women, and infants. Despite effective antivirals and vaccines, influenza is responsible on average for 226,000 excess hospitalizations and about 24,000 deaths each year in the United States alone. [1] The number of deaths is estimated to be over 500,000 worldwide.

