1.1.4 Treatment of Influenza

The U.S. CDC has recommended the following regarding the treatment of influenza:

<http://www.cdc.gov/h1n1flu/recommendations.htm#3>

Prompt empiric treatment is recommended for persons with suspected or confirmed influenza and:

- Illness requiring hospitalization
- Progressive, severe, or complicated illness, regardless of previous health status, and/or
- Patients at risk for severe disease

The following medical conditions have been associated with an increased risk of complications from influenza: [11]

- Asthma
- Neurological and neuro-developmental conditions [including disorders of the brain, spinal cord, peripheral nerve, and muscle such as cerebral palsy, epilepsy (seizure disorders), stroke, intellectual disability (mental retardation), moderate to severe developmental delay, muscular dystrophy, or spinal cord injury].
- Chronic lung disease (such as chronic obstructive pulmonary disease [COPD] and cystic fibrosis)
- Heart disease (such as congenital heart disease, congestive heart failure and coronary artery disease)
- Blood disorders (such as sickle cell disease)
- Endocrine disorders (such as diabetes mellitus)
- Kidney disorders
- Liver disorders
- Metabolic disorders (such as inherited metabolic disorders and mitochondrial disorders)
- Weakened immune system due to disease or medication (such as people with HIV/AIDS, or cancer, or those on chronic steroids)
- People younger than 19 years of age who are receiving long-term aspirin therapy

Additionally, for the 2009 H1N1 influenza, morbid obesity (body mass index [BMI] ≥ 40) has been suggested as an independent risk factor. [12]

The Infectious Diseases Society of America (IDSA) guidelines for influenza recommended treatment for persons who meet the following criteria:

- a. Persons with laboratory-confirmed or highly suspected influenza virus infection at high risk of developing complications within 48 hours after symptom onset.
- b. Persons requiring hospitalization for laboratory-confirmed or highly suspected influenza illness, regardless of underlying illness or influenza vaccination status, if treatment can be initiated within 48 hours after onset of symptoms.

They further state, treatment should be considered for both adults and children with influenza virus infection who meet the following criteria:

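### Exclusion item 2 has no bullet for people under 19 on long-term aspirin, a high-risk group in Section 1.1.4, although 18-year-olds are eligible

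*Protocol*

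**What the plan says.** The trial is meant for low-risk outpatients. Protocol Section 4.1 states: "The subject population includes those at low risk for complications and morbidity from influenza (as defined by the U.S. CDC", and inclusion criterion 2 in Section 4.3 sets the age range as "Age ≥ 18 and < 65 years of age".

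The background says who is not low risk. Section 1.1.1 opens its list with "People at higher risk include people 65 years and older, people of any age with certain chronic medical conditions" and goes on to pregnant women and infants. Section 1.1.4 reports a CDC recommendation of prompt empiric treatment for patients at risk for severe disease. It then introduces 11 bullets with "The following medical conditions have been associated with an increased risk of complications from influenza", the last of which is "People younger than 19 years of age who are receiving long-term aspirin therapy". It adds BMI of 40 or more in the text below.

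Exclusion item 2 in Section 4.5 turns this into a criterion. Its heading is "Presence of a medical condition(s) that has been associated with increased risk of complications from influenza", followed by 13 bullets. None of them mentions aspirin, and neither the rest of the protocol nor the SAP mentions it outside Section 1.1.4.

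**The concern.** The protocol names the under-19 aspirin group as being at increased risk but does not carry it into the operative list, while it admits 18-year-olds. Item 2 is otherwise a full transcription. It spells out groups that are not diseases (older age, pregnancy or recent postpartum, high BMI). It even includes "Age 65 years of age or older", which inclusion criterion 2 already rules out. Someone working from so detailed a list could reasonably take it as complete.

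What is at stake is subject protection. For pregnant women, Section 4.1.1 reasons that treatment is recommended and that "randomization of a pregnant woman to possibly receive placebo could not be justified". Section 1.1.4 puts the aspirin group among those at increased risk and reports a treatment recommendation for at-risk patients, so the same logic extends to that group. This extension is an inference, since the protocol does not state it. The documents do not describe the complication such subjects face, so the harm cannot be sized from them.

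**Working it through.** No sample-size or error-rate arithmetic applies. The check is a comparison of lists.

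**Step 1. Count the named risk groups.** Section 1.1.4 has 11 bullets and adds BMI ≥ 40 in text. Section 1.1.1 adds age 65 or older, pregnant women and infants. The chronic conditions in Section 1.1.1 fall within the Section 1.1.4 bullets and are not counted again. Total: 11 + 1 + 3 = 15.

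**Step 2. Match each group to item 2 of Section 4.5.**

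| Named risk group | Source | Bullet in item 2? |
|---|---|---|
| Asthma | 1.1.4 | Yes |
| Neurological and neuro-developmental | 1.1.4 | Yes |
| Chronic lung disease | 1.1.4 | Yes |
| Heart disease | 1.1.4 | Yes |
| Blood disorders | 1.1.4 | Yes |
| Endocrine disorders | 1.1.4 | Yes |
| Kidney disorders | 1.1.4 | Yes |
| Liver disorders | 1.1.4 | Yes |
| Metabolic disorders | 1.1.4 | Yes |
| Weakened immune system | 1.1.4 | Yes |
| Under 19 on long-term aspirin | 1.1.4 | **No** |
| BMI ≥ 40 | 1.1.4, text | Yes |
| Age 65 or older | 1.1.1 | Yes |
| Pregnancy | 1.1.1 | Yes (with 4 weeks postpartum) |
| Infants | 1.1.1 | **No** |

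Matched: 10 + 1 + 2 = 13, which uses up all 13 bullets. Unmatched: 15 − 13 = 2. Two matched bullets drop an example (intellectual disability under neurological conditions, sickle cell disease under blood disorders), but those groups still have their bullets.

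**Step 3. See whether another criterion closes either gap.** The minimum age of 18 excludes every infant. It does not exclude all people under 19, because age 18 is eligible. Exclusion items 1 and 3 to 10 do not address aspirin, and Section 5.8 prohibits only investigational medications. The aspirin group is therefore the only one with neither a bullet nor another criterion that excludes all of it.

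**Step 4. Look at the screening safeguards.** Section 6.3.1.3 records prescription and over-the-counter drugs used in the past 7 days. Section 6.3.1.4 calls for a brief examination for conditions that would raise the subject's risk. Section 6.3.2.1 has the investigator review all criteria. Each could bring aspirin use to light, but none ties it to exclusion.

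**Step 5. Bound the exposure.** The eligible single years of age run from 18 to 64: 64 − 18 + 1 = 47, and the group overlaps one of them. No age distribution is given, so 1 in 47 describes the overlap and is not an estimate of prevalence. The 50 pilot subjects were already randomized at Version 8, so a change could reach at most 560 − 50 = 510 subjects, less any main-study subjects already randomized. That number is not stated.

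**The case against.** The strongest reply is that the criterion already covers the group. The heading of item 2 nearly repeats the lead-in to the Section 1.1.4 list, where the aspirin group sits. Nothing says the bullets are exhaustive, and the population is defined as low risk by CDC criteria. On that reading an 18-year-old on long-term aspirin is already excluded. A miss would need a site to ignore the heading, treat the bullets as closed and overlook the drug history. The Manual of Operations is not available, so site tools may well name the group. Long-term aspirin at 18 also suggests an underlying disease, and heart, blood and immune conditions are excluded under their own bullets.

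Much of this stands. The intent to exclude is clear, and the chance of a miss cannot be shown to be more than slight. Overlap with other bullets could remove anywhere from none to all of these subjects; the documents do not say. But the heading speaks of a medical condition, whereas this group is defined by age and a drug, and item 2 gives its other non-disease groups their own bullets. Clear intent is a reason to make the list match the background. It does not make the list unambiguous for the person doing the screening.

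**Conclusion.** The point holds, as a minor improvement that could be made. Exclusion item 2 omits one group that the protocol itself calls high risk, and the age limit does not fully remove that group. Very few subjects are affected, and possibly none; the documents give no basis for a probability. There is no effect on power, endpoints, analysis or conclusions.

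That the bullet is missing is certain from the text. That a subject could be wrongly randomized depends on two assumptions: that some site treats the bullets as the complete list, and that site materials not available here do not name the group.

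**What to change.** At the next amendment, add one bullet to item 2 of Section 4.5: *Age younger than 19 years and receiving long-term aspirin therapy*. For 18-year-olds, check it against the 7-day medication history already taken under Section 6.3.1.3. Until then, a note telling sites that item 2 follows the whole Section 1.1.4 list would serve.

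The cost is one bullet and one line on the screening checklist, with no new data collection and negligible loss of accrual. Section 11.1 requires IRB/IEC approval before an amendment takes effect, and up to about 50 sites may take part. The change therefore does not warrant an amendment of its own and should ride on one made for other reasons.
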